Official Title of Study: -

**Virtual reality versus Biodex Training
in Adolescent Athletes with Chronic
Ankle Instability**

Document Date: - 4/10/2020.

**Human Subjects protection review board
approval date: -9/9/2020**

Virtual reality versus Bidex Training in Adolescent Athletes with Chronic Ankle Instability

PURPOSE:

This study aimed to assess the efficacy of virtual reality versus bidex training in adolescent athletes with chronic ankle instability.

BACKGROUND:

Ankle instability results from repetitive ankle sprains are common injuries in active young people. Most of these injuries recover quickly on their own, do not require imaging, and do better with early motion and rehabilitation. High ankle sprains and fractures are much less common but more serious. They may require imaging and more treatment.

Phases of rehabilitation for ankle sprain

Phase I treatment involves resting and protecting the ankle to permit healing, to prevent further injury, and to control pain and swelling.

Phase II treatment begins once pain and swelling have subsided to the point where the athlete can comfortably bear weight and walk from place to place.

Virtual reality (VR) is a simulated experience that can be similar to or completely different from the real world. Applications of virtual reality can include entertainment (i.e. video games) and educational purposes (i.e. medical or military training). Other, distinct types of VR style technology include augmented reality and mixed reality.

HYPOTHESES:

H0 there is no significance difference between virtual reality versus bidex training in adolescent athletes with chronic ankle instability.

H1 there is a significance difference between virtual reality versus bidex training in adolescent athletes with chronic ankle instability.

RESEARCH QUESTION:

Is there is no significance difference between virtual reality versus bidex training in adolescent athletes with chronic ankle instability?

Aim of the study:

To determine the effect of to assess difference between virtual reality versus bidex training in adolescent athletes with chronic ankle instability.

Inclusion criteria:

1. Children will have sustained lateral ankle sprain (grade II).
2. Their age was ranging from 12-16 years
3. Children participated in this study only males.
4. They will able to follow the verbal commands or instructions during testing.

Exclusion criteria:

1. Children with 1,2 grade of ankle sprain
2. Children with deformity in foot
3. Children with back problems.
4. Children with balance affection.

Methods for assessment:

- Balance assessment
 - Over All Stability Index
 - Antero-Posterior Stability Index
 - Medio-Lateral Stability Index (MLSI)

Methods for treatment:

Sixty patient with muscular dystrophy were enrolled in this study and were assessed for eligibility.

Group (A) received the traditional physical therapy program.

Group (B) received the traditional physical therapy program in addition to virtual reality.

Group (B) received the traditional physical therapy program in addition to bidex balance training.

All patients will received sessions three times / week for three successful months. Pulmonary function test were used to assess pulmonary functions pre and post intervention. All patients were assisted before and after three months of intervention.

RECRUITMENT

Please state clearly how the participants will be identified, approached and recruited.

Note: Attach a copy of any poster(s), advertisement(s) or letter(s) to be used for recruitment.

The patients will be recruited from Outpatient Clinic of faculty of medicine, South Valley University

CONSENT

Describe the process that the investigator(s) will be using to obtain valid consent. If consent is not to be obtained explain why. If the participants are minors or for other reasons are not competent to consent, describe the proposed alternate source of consent, including any permission / information letter to be provided to the person(s) providing the consent.

I am freely and voluntarily consent to participate in a research program under the direction of M.Sc.

A thorough description of the procedure has been explained and I understand that I may withdraw my consent and discontinue participation in this research at any time without prejudice to me.

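### The eligibility criteria do not select adolescent athletes with chronic ankle instability, and the passages on who is enrolled contradict each other

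*Protocol*

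**What the plan says.** The Purpose reads "This study aimed to assess the efficacy of virtual reality versus bidex training in adolescent athletes with chronic ankle instability". The title, both hypotheses, the research question and the aim name the same population. The Background ties the condition to recurrence: "Ankle instability results from repetitive ankle sprains".

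The inclusion criteria have four items:
1. "Children will have sustained lateral ankle sprain (grade II"
2. age 12 to 16 years
3. male sex
4. ability to follow instructions during testing

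Exclusion 1 removes "Children with 1,2 grade of ankle sprain". Exclusion 4, listed after foot deformity and back problems, removes "Children with balance affection". Methods for assessment has one heading, "Balance assessment", with three stability indices under it.

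Methods for treatment states: "Sixty patient with muscular dystrophy were enrolled in this study and were assessed for eligibility". The Recruitment section names one hospital outpatient clinic as the source and adds no condition on sport or instability.

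**The concern.** Screening staff work from the numbered criteria, and the criteria decide which patients the results describe. Here they omit both attributes that define the research question. A single sustained sprain is not chronic instability by the Background's own account, and nothing in the list asks about sport.

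The other passages do not settle the matter, because they point to different patients. Two things are at stake:

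- **Attribution.** Whatever the trial finds, it could not be taken as a finding about adolescent athletes with chronic ankle instability. This holds whichever way the result falls.
- **Sensitivity.** The Background says of these injuries: "Most of these injuries recover quickly on their own". Outcomes are taken after three months. Children without lasting instability could improve in every arm, which would pull the between-arm difference toward none.

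Exclusion 4 is a smaller problem. Its neighbours suggest that it means balance disorders of other origin. It carries no such limit, though, and read literally it removes children with the very deficit that the outcomes measure and the balance training targets. Different screeners could apply it differently.

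**Working it through.** **The text, side by side**

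| Place in the protocol | Who is described |
|---|---|
| Title, Purpose, Hypotheses, Research question, Aim | Adolescent athletes with chronic ankle instability |
| Inclusion 1 | Children with a grade II lateral sprain |
| Inclusion 2, 3, 4 | Age 12 to 16; male; can follow instructions |
| Exclusion 1 | Grade 1 and 2 sprains removed |
| Methods for treatment | Sixty patients with muscular dystrophy |
| Recruitment | Patients of one outpatient clinic |

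- Inclusion items that require chronic or recurrent instability: 0 of 4. None mentions recurrence, time since injury or a measure of instability.
- Inclusion items that require athlete status: 0 of 4.
- Inclusion 1 together with exclusion 1: grade II is both required and barred, so the eligible set is empty.
- If inclusion 1 prevails, a boy of 12 to 16 with one grade II sprain who plays no sport and has no lasting instability meets all four items, and no exclusion removes him.
- If exclusion 1 prevails, inclusion 1 has to be rewritten. The list would still contain no instability or athlete criterion.

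**Size: illustration only**

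The protocol gives no effect size, standard deviation, alpha, power or expected share of non-target participants, so it has no figure to reproduce. The following shows only how sensitive a comparison of this size could be.

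Inputs:
- 20 per arm = 60 / 3. The sixty comes from the muscular dystrophy sentence, and the equal split over the three groups is an assumption.
- Two-sided alpha of 5% and 80% power for a pure target population (assumed). By the noncentral t distribution for two groups of 20, this needs a true effect of d = 0.909 SD.
- *s* = share of participants outside the target population; *r* = fraction of the effect that they show (both assumed). The outcome SD is taken as unchanged.

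Formula: diluted d = 0.909 × [1 − s × (1 − r)]. For example, with s = 0.25 and r = 0: 0.909 × 0.75 = 0.682.

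| s | r = 0: d | power | r = 0.5: d | power | r = 1: power |
|---|---|---|---|---|---|
| 10% | 0.818 | 71% | 0.864 | 76% | 80% |
| 25% | 0.682 | 56% | 0.795 | 69% | 80% |
| 50% | 0.455 | 29% | 0.682 | 56% | 80% |

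With r = 0, restoring 80% power would take about 24.4, 34.8 or 76.9 per arm instead of 20.

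Starting instead from 80% power at 15 per arm (d = 1.060) or 30 per arm (d = 0.736) changes these power figures by no more than 0.1 percentage point. That is nearly built in, because d is solved again for 80% each time. It means only that the illustration does not depend on the doubtful sixty. No figure is given for exclusion 4.

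**The case against.** The best defence is that the title, purpose, hypotheses, research question and aim already set the base population, and that the numbered items merely restrict it further. A screener might read it that way. But no item says so, nothing in the protocol defines chronic instability or athlete, and the treatment section names another disease, so the title cannot simply be presumed to govern. This softens the omission without removing it.

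A second defence is that exclusion 1 and the muscular dystrophy sentence are slips or text carried over from elsewhere. That is plausible, but correcting both would still leave a list that admits a non-athlete with a single sprain. Nor would the unseen analysis plan be expected to cure this, since eligibility belongs in the protocol.

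Three points against the argument on harm do stand:

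- Dilution depends on inclusion 1 prevailing over exclusion 1. It also rests on a general Background remark that is not specific to grade II sprains or to the stability indices, and the sentence before it is garbled. Only the statement that such children could dilute the comparison is supported.
- The power figures carry no information specific to this trial. Every input except the sixty is assumed, and mixing recovered and unstable children could change the outcome SD. They should not decide how serious the point is.
- Exclusion 4 is an ambiguity of wording, not a proven contradiction.

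None of these affects the attribution problem, which needs no assumption about dilution.

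**Conclusion.** The concern holds, with high confidence, and the sponsor should act on it. Applied literally, the criteria admit no child. If inclusion 1 prevails, they admit children who need not be athletes or have chronic instability. In neither case can they support a conclusion about the population the trial names. This rests on the wording alone.

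The effect on power is not derivable from the document. In the illustration it runs from no loss, if non-target participants respond fully, to a fall from 80% to about 29%, if half of them show no between-arm difference. How many such children would enter, and how they would respond, is unknown. The exclusion 4 point is secondary, and the conclusion stands without it.

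**What to change.** - Add inclusion criteria for chronic ankle instability and for athlete status that match the stated aim, using the sponsor's own definitions.
- Reconcile inclusion 1 with exclusion 1 on sprain grade. Which grade is intended is for the sponsor to state.
- Correct the sentence in Methods for treatment that names muscular dystrophy.
- Limit exclusion 4 to balance disorders not due to the ankle condition, if that is what is meant.
- If the criteria stay as they are in substance, restrict the conclusion to the population they actually admit.

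The cost is protocol wording, history-taking at screening and review board approval. The added inclusion criteria would narrow recruitment by an unknown amount, possibly a substantial one with a single clinic named; limiting exclusion 4 would widen entry. Whether enrolment has begun is unclear, because the tenses are mixed and enrolment is reported as done only in the muscular dystrophy sentence. If it has begun, participants already entered should be reported against the new criteria. Restricting the conclusion costs wording only, but leaves the stated question unanswered.

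### Inclusion item 1 requires a grade II ankle sprain and exclusion item 1 excludes grades 1 and 2, so on a plain reading no child is eligible

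*Protocol*

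**What the plan says.** Under Inclusion criteria, item 1 reads "Children will have sustained lateral ankle sprain (grade II"). It is the only inclusion item about the injury; items 2 to 4 cover age, sex and the ability to follow instructions. Under Exclusion criteria, item 1 reads "Children with 1,2 grade of ankle sprain".

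Neither item names a grading scale, gives a time window, or says whether it means the index ankle or any ankle. The grade is a Roman numeral in one item and Arabic numerals in the other.

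No other section gives a sprain grade. The Purpose describes the population only by diagnosis: "This study aimed to assess the efficacy of virtual reality versus bidex training in adolescent athletes with chronic ankle instability". The Background says "Ankle instability results from repetitive ankle sprains are common injuries in active young people", without a grade or a time limit. Methods for treatment describes the enrolled patients by a different disease: "Sixty patient with muscular dystrophy were enrolled in this study and were assessed for eligibility". That is a separate problem, and the sentence does not help to settle the sprain grade.

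**The concern.** The grade that the inclusion list requires is one of the two grades that the exclusion list removes. If both rules are applied as written, nobody can be enrolled. Any enrolment therefore means that a written rule was ignored or an unwritten one was supplied, and the protocol does not say which.

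The choice matters because it fixes the injury severity of the children studied. Following inclusion item 1 alone admits grade II sprains. Following exclusion item 1 alone keeps those same children out. Two screeners acting in good faith could recruit groups with no child in common. A reader of the results could not tell from the protocol what severity of sprain the findings apply to. No analysis method can repair this afterwards; only a corrected rule, or recorded grades for the children actually enrolled, can.

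**Working it through.** The protocol has no figure to reproduce here. The check is set logic on two sentences.

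Inputs:
- Required grade: {2}, from Inclusion criteria, item 1 (II read as 2).
- Excluded grades: {1, 2}, from Exclusion criteria, item 1.

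Rule: a child is eligible on sprain grade if inclusion item 1 is met and exclusion item 1 is not met.

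| Sprain | Meets inclusion 1 | Meets exclusion 1 | Eligible |
|---|---|---|---|
| Grade 1 | no | yes | no |
| Grade II / 2 | yes | yes | no |
| Any other grade, or no sprain | no | no | no |

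Eligible cases: 0 of 3. In set form, {2} minus {1, 2} is empty.

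Ways in which a screener could still enrol someone, with the other criteria unchanged:

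1. Apply inclusion item 1 and ignore exclusion item 1: grade {2}.
2. Apply exclusion item 1 and ignore inclusion item 1: everything outside {1, 2}, including a child with no current sprain.
3. Read inclusion item 1 as a past sprain and exclusion item 1 as a current one: a past grade II sprain with no current grade 1 or 2 sprain. This set is not empty, but the distinction is an assumption that the protocol does not state.

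On the plain reading, routes 1 and 2 share no child, since {2} and the set outside {1, 2} do not intersect. Route 3 falls inside route 1 if route 1 is taken to cover past sprains, so those two may overlap heavily. The protocol selects none of the three, and the list need not be complete.

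**The case against.** The strongest reply is that the two items concern different times. Inclusion item 1 describes something that has already happened to the child, while exclusion item 1 describes a present state. The study is about chronic instability, and the Background attributes that to repeated sprains. On this reading the trial wants children with a past grade II sprain and no fresh one, and the contradiction disappears.

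The difference in tense is real and the reading is plausible. It does not rescue the text. Neither item states a past or current condition or gives an interval. Nor does the reading explain why only grades 1 and 2 would be excluded, since a current sprain of any other grade would then be no bar. A screener would still have to supply the rule.

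A second reply is that this is a misprint in one line. It may be, but nothing shows which line is wrong, and the two possible corrections select groups that do not overlap. A reader cannot safely make the repair.

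A third reply is that the population is still described as male adolescent athletes aged 12 to 16 with chronic ankle instability. That limits the consequence: what these two items leave undefined is the sprain grade, not every feature of the population. However, no eligibility item requires or defines chronic ankle instability, so the sprain item is the only inclusion item that describes the injury. It is also fair to say that no bias between the treatment groups follows from this. The damage is to eligibility and to the generalisability of the result.

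**Conclusion.** The contradiction stands. On the plain reading, 0 sprain grades satisfy both items, and the sprain grade of the enrolled children is not defined. This rests on two assumptions: that II and 2 denote the same grade, and that both items refer to the same sprain. Dropping the second can give a non-empty set, but only through a distinction that the protocol does not make.

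The number of children affected cannot be estimated, because the protocol gives no distribution of sprain grades. The point must be fixed because the rules, followed literally, enrol no one. Eligibility belongs in the protocol, so a separate analysis plan would not cure it.

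**What to change.** **Necessary.** The sponsor should reconcile the two items so that the target grade is not also excluded. If grade II is the target, exclusion item 1 has to change; if grades 1 and 2 were meant to be kept out, inclusion item 1 has to change. If the intended distinction is between a past and a current sprain, both items should say so. The documents do not show which of these was meant, and that decision is the sponsor's.

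**Advisable alongside it.** Name the grading scale, use one notation for grade in both items, and record and report each participant's sprain grade.

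**Cost.** If enrolment has not begun, the correction is one or two lines of text. Recording the grade adds one data item, which screeners need in any case to apply the rule. The protocol leaves enrolment status unclear: Methods for treatment says patients "were enrolled in this study and were assessed for eligibility", while Recruitment says "The patients will be recruited from Outpatient Clinic". If children have already been enrolled, an amendment cannot settle who was included, so their grades must be taken from screening records and reported. This change settles sprain grade only; the other parts of the population definition need their own correction.
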